6.3 Qualitative analysis

Qualitative interviews will be analysed using a framework approach, whereby data will be coded according to both theme and case, and then abstraction of themes and explanatory inferences will occur iteratively with codes, themes and inferences being quality checked by a second team members.

7. ETHICS

7.1 The intervention

Particular caution and attention must be taken when administering a new therapeutic intervention to monitor any potential negative reactions. Although psychological interventions generally have minimal harmful effects, there is still a slight risk involved. The skills training we developed is however based on a well-established treatment (DBT), and it has been adapted and used in BD, with no adverse reactions reported, and with good acceptability (Eisner et al., 2017; Goldstein et al., 2015; Van Dijk et al., 2013). Nevertheless, more robust studies are still needed, since most of these studies were pilots as well. Our programme seeks to follow the same principles, with some additional innovations, namely with specific skills to help upregulate and down regulate emotions in depressive/hypo/manic periods. If at any period a potential ethical issue arises from delivery of the treatment, the participants will be approached, and risk protocol will be put into place (according to the place where they are routinely followed). Information provided by participants as part of their treatment will be treated in confidence. Participants will be informed of the circumstances under which confidentiality may be broken and will be consulted with as far as possible if this should become necessary.

In addition, regarding the group session, a set of "ground rules" will be established at the pre-session, together with the facilitators. All group participants will be made aware that they should not divulge what is talked in the group, and at the same time they do not have to share any information in the group that they do not wish to. Due to the training approach and format of the group, which is not the same as a traditional therapeutic group, participants can discuss the material and exercises without having to share personal information if they do not wish to.

7.2 Use of randomisation

Participants will be informed of the randomisation procedure and that they have a fifty-fifty chance to receive the treatment. Since we are aware of the ethical issue underlying the allocation to a control group, and the possible frustration/disappointment of the participants for not being allocated to the

intervention group, we also make sure they know the importance of the randomisation for a future definitive trial, and this ensures the two groups do not differ systematically in their baseline characteristics. The participants are also informed they will be offered the possibility to do the programme after they finish their 6 month follow up assessment, so they have the same possibility as the experimental group.

7.3 Informed consent

At the initial contact with the research team, the study will be discussed, and patients asked whether they wish to move to the next stage (receiving the full information sheet and arranging a telephone research screening interview, with specific consent, if appropriate). If the patient indicates at this point – or later - that they do not wish to take part they will not be contacted further by the research team, other than to invite them to take part in a brief survey to ascertain their reasons for not taking part. If at the baseline assessment the patient wishes to consent to participation at that point the researcher will take consent and then proceed to the research assessment; if the patient does not wish to participate their involvement will finish at this point, and reasons will be noted. If the patient wishes to take more time to consider the study, the research assessment appointment will be rescheduled to allow sufficient time for them to consider their participation. Participants judged not to have capacity due to severe symptom levels will be reassessed at a later point convenient to them and directed the necessary care in the meantime.

7.4. Participant and researcher Risk

Inherent in the nature of the population under scrutiny is the risk of suicide. We will follow good clinical practice in monitoring for suicide risk during all research assessments with service-user participants. Risk to/from self or others, if detected, will be responded to in accordance with the established protocols established in the hospitals or association the participants are followed. Participants will be informed of any circumstances under which confidentiality may be broken.

7.5 Data Protection

Information collected in clinical assessment will be stored according to standard practice and GDPR advice, stored in a way that allows them to be easily traced and located if required, while making sure the paper documents are stored in locked cabinets and access is restricted to the people in the research team that need access. This documents will be stored in the hosting research center – CINEICC, in the building 2 facilities of the Faculty of Psychology and Educational Sciences, University of Coimbra. Information held on computers will be stored in a password protected location with codes

replacing personal data when possible. Original research records will be retained for 5 years, after which they will be retained in electronic form and original records destroyed. The electronic records will be kept for 10 years after the end of the study.

8. RESEARCH GOVERNANCE

The study will be conducted in compliance with the principles of the Declaration of Helsinki and in accordance with all applicable regulatory requirements for a study with its specifications. The University of Coimbra and its scientific committee will monitor its progress, and relevant contacts are provided for participants to contact in case they have any concerns regarding the study. The same agreement has been made with the hospitals and organisation collaborating with the study.

8.1 Monitoring and adverse events

All serious adverse events that are trial or treatment related will be recorded and immediately reported to the responsible investigator, and measures to be taken will be discussed. Additionally, in line with other studies, we will screen for adverse events that are not trial or treatment related and active withdrawals from treatment. We will also monitor if the participant changed their medication. Participants will be asked at their follow-up assessments if any adverse events happened since the beginning of their participation, or since the last assessment (in the 6 month follow up).

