4.1 General aims

We will also evaluate whether the following criteria have been met prior to planning a future definitive trial:

1. Trial participation does not lead to serious negative consequences (unexpected adverse reactions) for our participants.
2. Any serious concerns about the acceptability and feasibility of the trial procedures can be rectified prior to a full trial.
3. Follow-up data at 3 months is available from at least 60% of participants.
4. At least 60% of patients complete treatment (attend at least 50% of possible sessions).

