If the participant is eligible for the study, they will then complete the baseline self-report measures (see Appendix 3): measures assessed by the clinician will take place during the assessment (i.e. CIBD, YMRS and HMDS), and the self-report measure will be sent via link to be completed online. Participants in the experimental group will additionally fill in an adapted diary card and submit it once a week (between sessions), where they are asked to rate their emotions intensity and use of skills (see Appendix 4). Additionally, after each session participants will be asked to anonymously fill in the Group Session Rating Scale (GSRS; Duncan et al., 2003) which briefly assessed participants experience of the group regarding relationships in the group, goals and topics, approach/method, and overall cohesion. Following randomisation (more details in that section) participants will be followed up by the research team at 3 and 6 months post baseline. At 3 month follow up (post-randomisation) blinding was not

conducted considering the need to conduct a qualitative interview of the intervention programme. Independent clinicians and researchers conducted these interviews, and the qualitative interview was anonymised so that participants could share their experience freely about the facilitators, programme and group. All the assessment moments are described in Appendix 1 and the assessment measures per moment in Appendix 3.

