6. STATISTICAL CONSIDERATIONS

6.1 Sample Size

60 participants (30 per group) will allow us to address the stated objectives of this feasibility trial. This represents recruitment to Bi-REAL at full capacity (10 per group), with equivalent numbers randomised to TAU. Previous studies with this population estimate an attrition rate of 17% (with respect to the primary end point at nine months post-randomisation. Our sample size of 48 will allow us to estimate this level of attrition for a future definitive trial with a precision of $\pm 15\%$ with 95% certainty.

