6.2 Method of analysis

Given the feasibility objectives of this study, the initial focus of data analysis will be descriptive, regarding the enrolment data, attrition rates and treatment and study dropout. We will also describe the acceptability of the programme though the report of the programme assessment questionnaire and interview, along with the scores of the GSRS. The number of people completing the intervention will be reported and it is defined as attending at least 65% of group sessions, which corresponds to 8 sessions approximately). We will also report on the number who complete the research outcome measures alongside means and standard deviations regarding the number, length and frequency (time between) of sessions. All protocol deviations, along with reasons and number of missing items on questionnaires will be reported.

To address the other primary outcome (i.e., recovery and QoL) and informing future sample size estimation) levels of completion and mean and standard deviations (or equivalent) for all outcomes for both study arms will be reported at baseline, three and six months follow up, as will participant

rankings of personal value and relevance of clinical outcome measures. Additionally we expect to do linear mixed models analysis to explore the time x group interaction in the variables in study.

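### Only serious adverse events judged related must be recorded and reported at once, and neither the harm criterion nor the analysis section uses the rest

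*Combined protocol and SAP*

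**What the plan says.** Section 8.1 sets up two routes for adverse events. The first is for serious events: "All serious adverse events that are trial or treatment related will be recorded and immediately reported to the responsible investigator". The second is wider but slower: "we will screen for adverse events that are not trial or treatment related and active withdrawals from treatment". The only timing given is that "Participants will be asked at their follow-up assessments if any adverse events happened since the beginning of their participation", or since the previous assessment when the question is put at 6 months. The second route does not separate serious from other events and carries no duty of immediate reporting.

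Section 4.1 lists criteria to be checked before a definitive trial is planned. The first is: "Trial participation does not lead to serious negative consequences (unexpected adverse reactions) for our participants".

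Section 6.2 says that "the initial focus of data analysis will be descriptive, regarding the enrolment data, attrition rates and treatment and study dropout". It goes on to acceptability, treatment completion, missing items, protocol deviations, outcome summaries by arm and mixed models. Adverse events do not appear.

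On blinding, section 5.7 says: "At 3 month follow up (post-randomisation) blinding was not" carried out, because of the qualitative interview. No blinding is described for the 6-month visit or for judging whether an event is related.

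**The concern.** Relatedness works here as an entry condition for prompt reporting, when it could be a classification made afterwards. Criterion 1 then adds a second filter, because an event must be an attributed reaction and also unexpected. The protocol does not define related, unexpected or serious, and does not say who decides. In bipolar disorder a relapse or a suicidal act is easily put down to the illness, and section 7.4 itself treats suicide risk as inherent to this population. A harm caused by the programme could fail both filters and leave criterion 1 met. The information from the slower route would partly exist, but no stated decision or analysis would use it.

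**Working it through.** The documents give no figure for harm, so there is none to reproduce. The check is a reading of the rules against each other, followed by illustrations.

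**1. One event followed through the rules.** Take a serious worsening in an intervention participant early in the programme.
- If it is judged related, section 8.1 requires recording and immediate reporting, and criterion 1 counts it if it is also unexpected.
- If it is judged due to the illness, the immediate rule does not apply. The event surfaces, at the latest stated point, when the participant is asked at a visit. Criterion 1 does not count it, and section 6.2 does not tabulate it.

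One judgement, by an unnamed person, decides both how fast the event is reported and whether it counts.

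**2. Possible delay.** Assessments are at baseline, 3 and 6 months (section 5.1). An event just after baseline waits up to 3 − 0 = 3 months for the scheduled question. If the 3-month visit is missed, it waits up to 6 − 0 = 6 months. Criterion 3 accepts 3-month data from 60% of participants, so up to 0.40 × 60 = 24 could miss that visit. No route is stated for someone who misses both.

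**3. Unequal contact.** From section 5.5 and Appendix 2, the intervention arm is offered 1 pre-session + 12 sessions + 1 booster = 14 group contacts before 6 months. Up to 3 individual sessions bring this to 17. Participants also submit a weekly diary card with a mood rating and have email or message support. For treatment as usual, no study contact between assessments is described. Events learned outside the visits will therefore come mostly from one arm. That could make the intervention look worse, while attribution to the illness could make it look better.

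**4. What 30 per arm can support.** Section 6.1 gives the size: "60 participants (30 per group) will allow us to address the stated objectives of this feasibility trial". Event rates are not in the documents, so those below are assumptions.
- Zero events in one arm, upper limit 1 − a^(1/n): 1 − 0.05^(1/30) = 9.5% (one-sided 95%); 1 − 0.025^(1/30) = 11.6% (two-sided 95%).
- Half-width of the 95% interval for the difference at equal rates p, 1.96 × √(2p(1 − p)/30): 11.0 points at p = 5%, 15.2 at 10%, 20.2 at 20%.
- Power of a two-sided 5% Fisher exact test, by enumeration: 1.9% for 5% v 10%, 9.6% for 10% v 20%, 24.1% for 5% v 20%, 37.2% for 10% v 30%.

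The figures in step 4 depend on the sample size alone. They do not show the defect. They show that a by-arm table should be read descriptively and not tested.

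**The case against.** The strongest reply is that section 8.1 does not ignore events judged unrelated. It screens for them, tracks medication changes, and puts the adverse-event question at both follow-ups with no restriction by arm. Suicide risk is monitored at every research assessment (section 7.4). The clinician-rated mood scales are repeated at 3 and 6 months, with outcome summaries by arm (sections 5.10 and 6.2), so worsening is still measured. This stands, and it rules out any reading that such events are discarded. It does not supply prompt reporting, a place in criterion 1 or a table.

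Several stronger readings are tempting, and the documents do not support them:
- A reader might infer that a control-arm event can never qualify. The rule covers events related to the trial as well as to the treatment, and section 7.2 foresees disappointment at allocation to control.
- A reader might infer that relatedness is judged by someone who knows the arm. That is likely but not stated. Only the 3-month assessment is described as unblinded, and its interviewers are called independent.
- A reader might apply the 17% attrition in section 6.1 and conclude that about 10 of 60 (0.17 × 60 = 10.2) are never asked. That figure comes from previous studies with a nine-month endpoint, which this trial does not have. A person who misses 3 months can still report the event at 6.

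It can also be said that a feasibility criterion need not compare arms, and that 30 per arm could not settle the matter. That is fair against a test. It is no argument against recording and tabulating what happened.

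**Conclusion.** The point holds as a gap between sections 8.1, 4.1 and 6.2. Immediate reporting is limited to serious events judged related, the harm criterion counts only attributed and unexpected reactions, and no adverse-event analysis is planned. The consequence is a possible delay of about three to six months in learning of a serious event put down to the illness, and its absence from criterion 1. The number of events affected cannot be estimated, because the documents give no event rate. The 9.5% limit for 0 of 30 should not be read as information lost through attribution, since it would be the same after the change. The conclusion rests on the text as written and assumes no separate safety procedure outside it. The change should be made: it alters a stated rule, costs little, and bears on safety in a population that the protocol regards as at risk.

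**What to change.** - **Section 8.1:** delete the qualifier that limits the first sentence to events related to the trial or the treatment. Every serious adverse event in either arm is then recorded and reported to the responsible investigator on awareness. Make relatedness a separate field completed later, and state who completes it and whether that person knows the arm.
- **Section 6.2:** add a descriptive table by arm of all serious events from any source, giving events and participants with confidence intervals and no test. Show for each event whether it was learned from the scheduled 3- or 6-month question or from other contact. The scheduled-question events are the like-for-like comparison between arms.
- **Section 4.1:** judge criterion 1 on all serious events from any source together with that table, and not on attributed reactions alone. Restricting the criterion to the scheduled question would be a mistake, because it would drop serious events disclosed in sessions or occurring in people who miss the visit.

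The cost is wording in three sections and a few more event forms among 60 participants. The limitation to state is that, with 30 per arm, the comparison remains descriptive.

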9. FINANCE AND FUNDING

This study is funded by the Portuguese Foundation of Science and Technology (or: *Fundação para a Ciência e Tecnologia - FCT*), with the attribution of an individual doctoral scholarship (funder reference number: SFRH/BD/130116/2017).

10. CHANGES TO THE INITIAL PROJECT

Changes to the assessment procedures were done due to the pandemic Covid-19, which had implications in the recruitment strategies and the timings initially projected. This project proposal was adjusted and resubmitted to the ethics committee involved in the study and approved.

Appendix 2 : Bi-REAL: 12-Session DBt-ST programme for Bipolar Disorder Layout

MODULE	SESSION	CONTENT AND SKILLS	TARGET PROBLEMS / FOCUS
Pre-Session	0	DBT Assumptions General and personal Goals, Biosocial Theory for Bipolar Disorder	DBT Assumptions, Group Rules and confidentiality
Mindfulness	1	Wise mind What Skills: Observe, Describe, Participate	Understand the difference between emotion mind, reason mind and wise mind. Introduction to Mindfulness
	2	How Skills: Non-judgmentally, One-Mindfully, Effectively	Attention Focus, notice thoughts. Not reacting to urges and impulsive behavior
	3	Understand, Identify and Label emotions	Perception and processing of emotions
	4	Check the Facts, Opposite action	Behaviour and Cognitive Change
Emotion Regulation	5	Problem Solving	Skilfully make an action plan. Put emotions into action
	6	CAMARAS – managing highs and lows	Knowing what to do when a mood change arises.
	7	ABC PLEASE Skills Build Mastery Cope ahead	Managing vulnerability to emotions Anticipate reactions, plan
Distress Tolerance	8	TIPP, Managing Extreme emotions	Managing extreme mood states, prevent impulsive reactions. Focusing attention
	9	Distract, Self-Soothe, Radical Acceptance	Capacity to tolerate difficult emotions
	10	DEAR MAN (Describe, Express, Assert, Reinforce; Mindful, Appear Confident, Negotiate)	Managing situations that cue emotions
Interpersonal Effectiveness	11	GIVE FAST (Gentle, act Interested, Validate, Easy manner)	Relationship and Self-respect effectiveness
	12	Validation Review what was learned, what to take home.	Review of the program and intention to continue training skills.

Appendix 3: Timing of Measures Completed by Participants

Table 1 - Schedule of participants' assessment

	Pre-intervention		During Intervention ²		Post-intervention	
	Screening	Baseline	Each session	Post-treatment	3 months follow-up	
Clinical Interview for Bipolar Disorder (CIBD)	✓	✓		✓		✓
Demographics (e.g. Age, education, employment)		✓				
Clinical History (e.g., family history of mood disorder, age of onset, number of affective episodes, hospitalisation)		✓				
Hamilton Rating Scale for Depression (HMDS)		✓		✓		✓
Young Mania Rating Scale (YMRS)		✓		✓		✓
Quality of Life in Bipolar Disorder (QOL-BD)		✓		✓		✓
Bipolar Recovery Questionnaire (BRQ)		✓		✓		✓
Multidimensional assessment of thymic states (MATHYS)		✓		✓		✓
Distress Tolerance Scale (DTS)		✓		✓		✓
Depression Anxiety and Stress Scale (DASS-21)		✓		✓		✓
Difficulties in Emotion Regulation Questionnaire (DERS)		✓		✓		✓
Philadelphia Mindfulness Scale (PHLMS)		✓		✓		✓
External and Internal Shame Scale (EISS)		✓		✓		✓
Rumination-Reflexion Questionnaire (RRQ-10)		✓		✓		✓
Forms of Self-Criticising/Attacking & Self-Reassuring Scale (FSCRS)		✓		✓		✓
The group session rating scale (GSRS) ²			✓			
Bi-REAL Diary card ² (Appendix 4)			✓			

² Only for the Experimental Group

Appendix 4: Diary card (1/2)

Diary Card

Week overall assessment	Mood	Sleep	Adherence to medication		
			Did you take your medication as prescribed?		
	-5 to +5	Mean number of hours daily:	Yes	No	Only part of it
Week 1					
Mood Scale:					
-5 = Extremely depressed/ the more depressed I have ever been 0 = Stable Mood (neither depressive nor hypo/maniac) 5 = Extremely hypo/maniac (the most maniac I have ever been)					

Instructions: Mark the days where you used the following skills

Mindfulness	1. Wise Mind	Monday	Tuesday	Wednes.	Thurs	Friday	Sat	Sun
	2. Observe	Monday	Tuesday	Wednes.	Thurs	Friday	Sat	Sun
	3. Describe	Monday	Tuesday	Wednes.	Thurs	Friday	Sat	Sun
	4. Participate	Monday	Tuesday	Wednes.	Thurs	Friday	Sat	Sun
	5. Non-judgemental	Monday	Tuesday	Wednes.	Thurs	Friday	Sat	Sun
	6. One mindfully	Monday	Tuesday	Wednes.	Thurs	Friday	Sat	Sun
	7. Effectively	Monday	Tuesday	Wednes.	Thurs	Friday	Sat	Sun
Emotional Regulation	8. Identify and name emotions	Monday	Tuesday	Wednes.	Thurs	Friday	Sat	Sun
	9. Check the Facts	Monday	Tuesday	Wednes.	Thurs	Friday	Sat	Sun
	10. Opposite Action	Monday	Tuesday	Wednes.	Thurs	Friday	Sat	Sun
	11. Problem Solving	Monday	Tuesday	Wednes.	Thurs	Friday	Sat	Sun
	12. Accumulate Positives	Monday	Tuesday	Wednes.	Thurs	Friday	Sat	Sun
	13. Build Mastery	Monday	Tuesday	Wednes.	Thurs	Friday	Sat	Sun
	14. Cope ahead	Monday	Tuesday	Wednes.	Thurs	Friday	Sat	Sun
Distress Tolerance	15. CAMERAS	Monday	Tuesday	Wednes.	Thurs	Friday	Sat	Sun
	16. STOP	Monday	Tuesday	Wednes.	Thurs	Friday	Sat	Sun
	17. TIPP	Monday	Tuesday	Wednes.	Thurs	Friday	Sat	Sun
	18. ACCEPTS	Monday	Tuesday	Wednes.	Thurs	Friday	Sat	Sun
	19. Self-Soothing	Monday	Tuesday	Wednes.	Thurs	Friday	Sat	Sun
	20. Redirect the mind	Monday	Tuesday	Wednes.	Thurs	Friday	Sat	Sun
	21. Open hand, half smile	Monday	Tuesday	Wednes.	Thurs	Friday	Sat	Sun
Interpersonal Effectiveness	22. Radical Acceptance	Monday	Tuesday	Wednes.	Thurs	Friday	Sat	Sun
	23. DEAR MAN	Monday	Tuesday	Wednes.	Thurs	Friday	Sat	Sun
	24. GIVE FAST	Monday	Tuesday	Wednes.	Thurs	Friday	Sat	Sun
	25. Interpersonal Validation	Monday	Tuesday	Wednes.	Thurs	Friday	Sat	Sun

